2. RESEARCH OBJECTIVE

2.1 Primary objectives:

1. To determine whether proposed oral high dose vitamin D3 is sufficient for achieving the physiological concentration in HIV positive patients on ART. (primary outcome)

2.2 Secondary objectives:

1. To determine whether this intervention also improves CD4 count, viral load count, liver enzyme in study participants. (Efficacy outcome).
2. To discover whether this interventional regimen is safe and well tolerated by study participants. (Safety outcome).
3. To ascertain socio-demographics factors responsible for decreased level of vitamin D3 in HIV positive patients on ART.

2.3 Tertiary objectives:

1. To conclude the effects of total leucocytes count in HIV patients with vitamin D supplementation.
2. To determine the effects of total neutrophil count in HIV patients with vitamin-D supplementation.
3. To investigate the effects of total basophil count in HIV patients with vitamin-D supplementation.
4. To determine the effects of total eosinophil count in HIV patients with vitamin-D supplementation.
5. To conclude the effects of total monocyte count in HIV patients with vitamin-D supplementation.
6. To establish the effects of total platelets count in HIV patients with vitamin-D supplementation.
7. To find out the effects of total hemoglobin count in HIV patients with vitamin-D supplementation.
8. To determine the effects of total lymphocytes count in HIV patients with vitamin-D supplementation.

3. Study Population

Patients who visited the VCCT center of GOVT Said Mitha Teaching Hospital Lahore and the treatment center of Jinnah hospital HIV clinic were the study population and they were HIV positive and on ART. The study population consisted of HIV patients ranging in age from 19 to 50 years. Patients with severe vitamin D3 deficiency were seen at the multi-centric outpatient HIV department.

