3.1 Eligibility Criteria

Inclusion criteria:

- Age at enrolment between 19-50 years old
- Vitamin D deficiency level >20ng/ml
- Had not been taking any kind of vitamin D supplementation mega doses for since six months
- Written consent was signed by participants voluntarily

Exclusion criteria

- Pregnant women
- Vitamin D level <20ng/ml or taking vitamin D supplementation mega doses since last three months were not included

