4. STUDY PROCEDURES

4.1 Study Population

Patients visiting Said Mitha Teaching Hospital Lahore will be the study population and having diagnosed with HIV positive patients.

4.2 Sampling technique:

Random list was generated for the double blind purpose. This list was generated through Excel sheet.

4.3 Ethical Consideration:

The study will be conducted after approval from the Punjab University Ethical Review Board. Permission will also be obtained from Punjab AIDS Control Programme to use health facilities and this study will be registered at Clinical Trial.gov, to use the health facilities and services of paramedics staff for data collection. Written consent of parents and guardians will be taken before starting the study.

4.4 Data Collection:

All staff involved in the study will be trained by the principal investigator before start of data collection. Trained laboratory technician will screen the patients aged 19 years to 50 years of age in (VDT) diagnostic center of hospital visiting outpatients department in their community and will refer the positive patients to treatment center of AIDS Control Programme clinic of Mayo Hospital Lahore, After receiving their prescribed ART, the two positive groups would be divided into two equal groups, one group will receive 25hydroxy vitamin –D and other halves will receive placebo at the same time once weekly for 12 weeks. Patients will be called for follow-up after every

4 weeks. At the end, we will perform posttest and check the level of 25 hydroxy in both groups and other parameters and by using logistic regression we will evaluate the results of effectiveness of 25 hydroxyin blood levels of HIV patients

4.5 Randomization:

The random allocation sequence will be generated in an excel spread sheet by a statistician who will be independent of the study. Consecutive numbers will be assigned to active vs. placebo in equal numbers. No restrictions (e.g. stratification, block size) will be applied. This sequence will be used by the study pharmacy to label pairs of syringes containing active and placebo medication with a study number assigned to active and placebo arms, respectively. These staff will assign the consecutive ID numbers to participants according to the sequence in which they are enrolled, and the hospital pharmacy then supply syringes of placebo active medication bearing this ID number.

4.6 Blinding:

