6. STUDY SCHEDULE

Schedule of clinical assessment and procedure:

	Screening	Treatments			
	V 1 Screening & Assessment	V 2 Randomization & 1 st Dose	V 3 2 nd dose	V 4 3 rd dose	V 5 Post Assesments
	-7~1	1 Day	5 week	12 week	24 week
ICF	×				
Eligibility Criteria	×	×			
Baseline Questionnaire	×				
Weight	×		×	×	×
Height	×		×	×	×
Vital Signs	×	×	×	×	×
Vit-D	×			×	
				V4+1 Day	
CD4 count	×			×	
				V4+1 Day	
Viral load	×			×	
				V4+1 Day	
PCR	×			×	
				V4+1 Day	
CBC	×			×	
				V4+1 Day	
Study Medication		×	×	×	
AE Monitoring		×	×	×	×
RDA					×
End of Study					×

6.1 STUDY PROCEDURES AND ASSESSMENTS:

Visit Schedule:

Visit 1 (Screening, Days -3 to 1)

Subjects who were informed about the study and voluntarily gave written consent to participation had the following tests.

- a. Informed consent and screening number assignment
- b. Demographics

- c. Information on exposure to HIV infection
- d. Medical history
- e. Previous HIV lab test if any
- f. RT-PCR
- g. Laboratory tests
- h. Prior medications and therapies
- i. Physical examination (investigator questioning)
- j. Symptoms
- k. Body weight measurement
- l. Assessment of the inclusion/exclusion criteria

Visit 2 (Randomization, Baseline, Day 1):

- a. Medical history
- b. Prior medications and therapies
- c. Physical examination (investigator questioning)
- d. RT-PCR
- e. Laboratory tests
- f. Symptoms
- g. Assessment of the inclusion/exclusion criteria
- h. Randomization
- i. Prescription of test drug or placebo

Visit 3 (Day 4)

- a. Concomitant medications and therapies
- b. Physical examination (investigator questioning)
- c. RT-PCR
- d. Symptoms

e. Treatment adherence.

Visit 4 (Day 7):

a. Concomitant medications and therapies

b. Physical examination (investigator questioning)

c. RT-PCR

d. Laboratory tests

e. Symptoms

Visit 5 (Day 14)

a. Concomitant medications and therapies

b. Physical examination (investigator questioning)

c. RT-PCR

d. Laboratory tests

e. Symptoms

f. Body weight measurement

g. Adverse events

Visit 6 (Day 28):

a. Physical examination (investigator questioning)

b. Laboratory tests

c. AEs

d. Collection of clinical treatment information

Even if a subject was withdrawn, unless the subject withdrew the consent for safety follow-up, the safety follow-up was conducted at the scheduled visits (Visits 3, 4, 5, and 6) to collect the following clinical treatment information.

e. Treatment adherence

Unscheduled Visit:

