- 2.** Human immunodeficiency virus (HIV) is a key challenge for global health. Vitamin D deficiency is common in people living with HIV infection. Antiretroviral therapy (ART) may create unique risk factors for vitamin D insufficiency, including alterations of vitamin D metabolism by ART. Vitamin D supplementation in HIV-infected patients have not previously been investigated in Pakistan and it is unknown whether sufficient physiological levels is associated with improved clinical outcome or not. This statistical analysis plan (SAP) will give more detailed descriptions of the endpoints in the study and the corresponding analyses.

- 3. Study design:** We have designed this study with the hypothesis, that the addition of high dose of vitamin D supplementation would be effective in elevating serum 25-hydroxy vitamin D concentration into normal physiological range in patients with HIV infection and this would improve their clinical outcome over the period of 6 months' treatment. The primary outcome of the study will be the sufficient elevating level of serum 25-hydroxyvitamin D at 24weeks. Secondary outcome of the study will be, the increase means CD4 count, decrease in viral load and improvement in liver function test and to reduce the severity of clinical symptoms. This is a double-blind randomized placebo-controlled trial. 114, patients aged (19-50) years with diagnosed HIV disease will be recruited by purposive sampling technique from VCCT treatment centre of Government Said Mitha Teaching Hospital located in the walled city of Lahore, Pakistan. The patients will be divided into two arms. Arm-A patients will receive recommended ARV + Vitamin D supplements and patients in Arm-B will receive recommended ARV and placebo. Participants will be randomly allocated to receive 25 hydroxy vitamin D supplementation (n=) or placebo (n=) with the start of ART

	Screening	Treatments			
	V 1 Screening & Assessment	V 2 Randomization & 1 st Dose	V 3 2 nd dose	V 4 3 rd dose	V 5 Post Assessments
	-7~1	1 Day	5 week	12 week	24 week
ICF	×				
Eligibility Criteria	×	×			
Baseline Questionnaire	×				
Weight	×		×	×	×
Height	×		×	×	×
Vital Signs	×	×	×	×	×
Vit-D	×			×	
CD4 count	×			×	
Viral load	×			×	
PCR	×			×	
CBC	×			×	
Study Medication		×	×	×	
AE Monitoring		×	×	×	×
RDA					×
End of Study					×

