3.1 Sample size calculation

Assuming that 60% of patients in the control arm would attain > 30% of their baseline vitamin-D status at 6 months, we calculated that a total of 94 participants (47 per arm) would need to complete follow-up in order to detect a 25% absolute increase (to 85%) in the proportion of patients attaining > 30% vitamin-D level at 6 months in the intervention arm with 80% power at the 5% significance level. (Lake, Vitamin D in HIV-Infected Patients on HAART, 2014).

This number was inflated to a total of 114 to allow for attrition due to death and loss to follow-up. No interim analysis was performed. (Shriver, 2019)

4. Aims and objectives:

Primary objectives

1. To determine whether proposed oral high dose vitamin D3 is sufficient for achieving the physiological concentration in HIV positive patients on ART. (primary outcome)

Secondary objectives

1. To determine whether this intervention also improves CD4 count, viral load count, liver enzyme in study participants. (Efficacy outcome).
2. To discover whether this interventional regimen is safe and well tolerated by study participants. (Safety outcome).
3. To ascertain socio-demographics factors responsible for decreased level of vitamin D3 in HIV positive patients on ART.

Tertiary objectives:

1. To conclude the effects of total leucocytes count in HIV patients with vitamin D supplementation.
2. To determine the effects of total neutrophil count in HIV patients with vitamin-D supplementation.
3. To determine the effects of total eosinophil count in HIV patients with vitamin-D supplementation.
4. To conclude the effects of total monocyte count in HIV patients with vitamin-D supplementation.
5. To establish the effects of total platelets count in HIV patients with vitamin-D supplementation
6. To find out the effects of total hemoglobin count in HIV patients with vitamin-D supplementation
7. To determine the effects of total lymphocytes count in HIV patients with vitamin-D supplementation
8. To see if the effects of total HCT count in HIV patients with vitamin-D supplementation

5. Outcomes

This section will present the outcomes investigated to answer the study aims and objectives. The analyses are described in section 6 Analyses.

5.1 Primary outcome:

1. To determine whether proposed oral high dose vitamin D3 is sufficient for achieving the physiological concentration in HIV positive patients on ART. (primary outcome)

5.2 Secondary outcomes:

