7.2 Secondary Outcomes

The secondary outcome analysis will be performed to check the difference change in Placebo group and Active Treatment group (Vitamin-D Group) through comparing mean difference from Visit 1 to Visit 4. This test will identify the mean increase or decrease in the respective variables including CD4 count, PCR detection, Viral Load and Liver Enzymes change.

For the safety objective we will use only frequency/number of events to present it.

For the Socio-Demographic factors association or correlation chi square test or bivariate correlation will be checked with one constant variable (Low Vitamin-D Level on Visit 1).

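### The plan does not settle whether participants are new to ART or already established on it, and if both enter, the SAP's unadjusted CD4 and viral-load comparisons lose precision

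*SAP*

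**What the plan says.** On ART status the current text points two ways.

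- **At the start of ART.** The protocol abstract and SAP section 3 both say that participants are allocated to vitamin D "or placebo (n=) with the start of ART".
- **Already on ART.** Protocol section 3 says of the study population that "they were HIV positive and on ART". The primary objective in both documents, repeated as the primary outcome in SAP 5.1, concerns "achieving the physiological concentration in HIV positive patients on ART". The SAP therefore disagrees with itself as well as with the protocol.
- **Either.** Protocol 4.4 describes people who screen positive, are referred, and are then allocated: "After receiving their prescribed ART, the two positive groups would be divided into two equal groups". No duration of ART is given.

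Protocol 3.1 opens with "Age at enrolment between 19-50 years old" and goes on to vitamin D level, previous supplementation, consent and pregnancy. It has no criterion on ART status, duration or regimen. Protocol 4.5 says of the randomisation that "No restrictions (e.g. stratification, block size) will be applied".

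For the secondary outcomes, SAP 7.2 compares the arms on the "mean increase or decrease in the respective variables including CD4 count, PCR detection, Viral Load and Liver Enzymes change" between Visit 1 and Visit 4. SAP section 7 names the test: a t-test for two independent samples, or a non-parametric test if normality fails. There is no covariate, and SAP 6.2 has no subgroup by ART status. Protocol section 7, by contrast, specifies linear regression adjusted for the baseline value for continuous outcomes measured at baseline and at the end. It also names a Wilcoxon test. The SAP does not carry the regression forward.

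**The concern.** Protocol 8.3 says that ART is given to suppress the virus as far as possible. A patient who starts ART around Visit 1 should therefore show a fall in viral load, and probably a rise in CD4, from ART alone over the roughly 12 weeks to Visit 4. A patient already suppressed has little viral load left to lose. If both kinds are randomised, the spread of change in the pooled sample includes the distance between the two groups as well as ordinary variation between patients. An unadjusted test on change counts that distance as noise.

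Two things are at stake. The first is interpretation: as written, a reader cannot tell whether the secondary efficacy results describe people beginning ART, people established on it, or both. The second is precision in the CD4 and viral-load comparisons, which the sample size was not calculated for in the first place.

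**Working it through.** **The plan's own figure.** SAP 3.1 plans 47 completers per arm to detect 60% against 85% with 80% power at the 5% level. With a two-sided test and unpooled variance:

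n = (1.960 + 0.842)² × (0.60×0.40 + 0.85×0.15) / 0.25² = 7.849 × 0.3675 / 0.0625 = 46.2, so 47 per arm.

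This agrees exactly. It concerns the vitamin D responder outcome and is not disturbed by the present point. It is used below only as the number of patients per arm.

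**Inputs for CD4.** The documents give none of these, so all three are assumptions:

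- SD of CD4 change within each kind of patient: 100 cells
- Gap *d* in mean change between starters and established patients: 50 to 150 cells
- Share *f* of starters: 25% to 75%

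**Formula.** The variance of change in the mixed sample is SD² + f(1−f)d². The ratio to the unmixed variance is 1 + f(1−f)d²/SD², and the standard error grows by its square root. Because f(1−f) is the same at 25% and 75%, one row serves both. The last column takes an effect that would have 80% power at 47 per arm without mixing, 2.802 × 100 × √(2/47) = 57.8 cells, and gives Φ(2.802/√ratio − 1.960).

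| Share of starters | Gap (cells) | Variance ratio | Standard error | Power, if 80% without mixing |
|---|---|---|---|---|
| 25% or 75% | 50 | 1 + 0.1875×0.25 = 1.047 | +2% | 78% |
| 25% or 75% | 100 | 1 + 0.1875×1.00 = 1.188 | +9% | 73% |
| 25% or 75% | 150 | 1 + 0.1875×2.25 = 1.422 | +19% | 65% |
| 50% | 50 | 1 + 0.25×0.25 = 1.063 | +3% | 78% |
| 50% | 100 | 1 + 0.25×1.00 = 1.250 | +12% | 71% |
| 50% | 150 | 1 + 0.25×2.25 = 1.563 | +25% | 61% |

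**Type I error and recovery.** A simulation with 47 per arm, unstratified randomisation and 20,000 runs per setting used gaps from 0 to 3 SD. The unadjusted t-test kept a type I error rate of 4.8% to 5.1%. Adding ART status as a covariate brought power back to about 79% in every mixed setting.

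**Viral load.** The same argument applies, but I give no figure. The formula assumes equal spread in both kinds of patient, and that is a poor assumption when one group sits near the detection limit.

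**The case against.** The strongest reply is that there may be no mix at all. Someone who has just begun ART is both on ART and randomised at its start, and the route in Protocol 4.4, from screening through referral and first ART to allocation, can be read as describing new starters only. On that reading the extra variance disappears. This stands as a limit on the size of the point. A reader might infer from the two wordings that the trial did pool very different patients, but the documents only permit that. The contradiction remains, because Protocol section 3 describes clinic patients already on ART and Protocol 3.1 excludes neither kind.

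A reader might also infer bias or false positives. Neither follows: allocation is randomised, so ART status is balanced on average and the 5% level holds.

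It can be said, too, that the protocol already has a baseline-adjusted model. It does, and that model would recover part of any loss, since baseline viral load probably tracks ART status. But the SAP replaces it with an unadjusted test.

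Finally, a reader might expect an analysis restricted to patients with detectable virus at Visit 1 to restore power for virological response. It would not. Assume half are suppressed at Visit 1, with rates of 70% against 90% among the rest. Power for comparing proportions undetectable is then about 40% in all 47 per arm and 41% to 43% in the 23 or 24 per arm who were detectable. The loss comes from having fewer informative patients. The SAP does not specify a comparison of proportions in any case.

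**Conclusion.** The point holds in a conditional form. The conflict over ART status is in the current text of both documents, and the eligibility criteria do not resolve it. If new starters and established patients both enter, the SAP's unadjusted comparison of CD4 change has a standard error about 2% to 25% larger than it need be (variance 5% to 56%), under the assumed SD of 100 cells, gap of 50 to 150 cells and 25% to 75% starters. At the low end this is minor. At the high end it takes a comparison with 80% power to about 61%. If only one kind of patient enters, no precision is lost this way, and what remains is an undefined population and wording to correct.

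The consequence is confined to precision and interpretation of secondary outcomes. The planned 47 per arm for vitamin D is untouched. Protocol 1.2 says that two ART classes may enhance vitamin D metabolism, which is a further reason to record regimen, but it gives no size and supports no claim that the primary comparison is compromised.

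**What to change.** 1. Reconcile the passages on ART status (protocol abstract, Protocol sections 2, 3 and 4.4, SAP sections 3, 4 and 5), and state in Protocol 3.1 whether new starters, established patients or both are eligible, with a definition of each. Which population is intended is for the sponsor to say.
2. In SAP 7.2, replace the unadjusted test for CD4 and log viral load with the regression of Protocol section 7: Visit 4 value on arm and baseline value.
3. If both kinds of patient are admitted, add ART status (new or established) as a covariate in those models.
4. Record ART start date and regimen explicitly under the Visit 1 item "Prior medications and therapies". That item is generic and the Research Performa has no ART field, so it cannot be assumed that these data are already captured.
5. Virological response among those detectable at Visit 1 may be reported to make the question clear, but should not be presented as recovering power.

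The cost is wording in both documents, one more covariate (one degree of freedom) in the secondary models, and one more recorded item. If enrolment has finished, the covariate can still be added wherever ART start dates can be retrieved from clinic records.

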3.1 Sample size calculation

Assuming that 60% of patients in the control arm would attain > 30% of their baseline vitamin-D status at 6 months, we calculated that a total of 94 participants (47 per arm) would need to complete follow-up in order to detect a 25% absolute increase (to 85%) in the proportion of patients attaining > 30% vitamin-D level at 6 months in the intervention arm with 80% power at the 5% significance level. (Lake, Vitamin D in HIV-Infected Patients on HAART, 2014).

This number was inflated to a total of 114 to allow for attrition due to death and loss to follow-up. No interim analysis was performed. (Shriver, 2019)

4. Aims and objectives:

Primary objectives

1. To determine whether proposed oral high dose vitamin D3 is sufficient for achieving the physiological concentration in HIV positive patients on ART. (primary outcome)

Secondary objectives

1. To determine whether this intervention also improves CD4 count, viral load count, liver enzyme in study participants. (Efficacy outcome).
2. To discover whether this interventional regimen is safe and well tolerated by study participants. (Safety outcome).
3. To ascertain socio-demographics factors responsible for decreased level of vitamin D3 in HIV positive patients on ART.

Tertiary objectives:

1. To conclude the effects of total leucocytes count in HIV patients with vitamin D supplementation.
2. To determine the effects of total neutrophil count in HIV patients with vitamin-D supplementation.
3. To determine the effects of total eosinophil count in HIV patients with vitamin-D supplementation.
4. To conclude the effects of total monocyte count in HIV patients with vitamin-D supplementation.
5. To establish the effects of total platelets count in HIV patients with vitamin-D supplementation
6. To find out the effects of total hemoglobin count in HIV patients with vitamin-D supplementation
7. To determine the effects of total lymphocytes count in HIV patients with vitamin-D supplementation
8. To see if the effects of total HCT count in HIV patients with vitamin-D supplementation

5. Outcomes

This section will present the outcomes investigated to answer the study aims and objectives. The analyses are described in section 6 Analyses.

5.1 Primary outcome:

1. To determine whether proposed oral high dose vitamin D3 is sufficient for achieving the physiological concentration in HIV positive patients on ART. (primary outcome)

5.2 Secondary outcomes:

1. To determine whether this intervention also improves CD4 count, viral load count, liver enzyme in study participants. (Efficacy outcome).
2. To discover whether this interventional regimen is safe and well tolerated by study participants. (Safety outcome).
3. To ascertain socio-demographics factors responsible for decreased level of vitamin D3 in HIV positive patients on ART.

5.3 Tertiary outcome:

1. To conclude the effects of total leucocytes count in HIV patients with vitamin D supplementation.
2. To determine the effects of total neutrophil count in HIV patients with vitamin-D supplementation.
3. To determine the effects of total eosinophil count in HIV patients with vitamin-D supplementation.
4. To conclude the effects of total monocyte count in HIV patients with vitamin-D supplementation.
5. To establish the effects of total platelets count in HIV patients with vitamin-D supplementation
6. To find out the effects of total hemoglobin count in HIV patients with vitamin-D supplementation

7. To determine the effects of total lymphocytes count in HIV patients with vitamin-D supplementation
8. To see if the effects of total HCT count in HIV patients with vitamin-D supplementation

Other blood laboratory parameters

Vitamin-D level, CD4 count, viral Load, PCR, CBC

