Patients of all study participants will be blinded to allocation, as will be the doctors and the staff nurse who will enrol participants and perform study assessments. Active and placebo medication will be presented identically in 1 ml syringes, and will have identical appearance and texture.

4.7 Interventions:

All participants will be treated with vitamin D supplements (Annexure attached) provided by AIDS Control Programme at outpatients department according to WHO guidelines. Vitamin D and calcium will be supplied to HIV positive patients according to the study (Annexure attached) on a weekly basis by suitably trained staff

who will provide information regarding benefits of vitaminD advise as to how it should be taken. Participants who will be randomised to the intervention arm of the trial will receive one oral dose of 100,000 IU (10 mg) vitamin D3 (cholecalciferol) in 1 ml olive oil, will administer via a syringe at 5 and 12 weeks' post-initiation of vitamin D3 supplementation. Participants who will randomised to the control arm of the trial will receive one oral dose of placebo (1 ml extra virgin) via a syringe at 5 and 12 week's post-initiation of vitamin D3 supplementation. After screening further dose of RDA Vitamin-D will be provided for next 5 weeks to complete 24 weeks of study.

5. LAB ANALYSIS AND COLLECTION OF BLOOD SAMPLE:

25-hydroxyvitamin D concentration will be measured 0 and 60 days to assess baseline deficiency and then effect of supplementation, 3ml blood sample will be taken in gel tube after clot formation will be centrifuged. Serum or plasma may be stored for up to 3 days at 2-8 centigrade. Initially **Alere** HIV combo strips will be used for screening of HIV and syphilis, then on positive result we will use second screening on uni-gold HIV strip. Then on third step we will use SD HIV 1/2 3.0 strip for final confirmation of screening step and finally we perform RT-PCR at last.

The haemoglobin level will be determined at 0 days and 60 days to assess the anaemia and effect of supplementation in all selected participants. Blood sample will be drawn from patients who will give their consent voluntarily.

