6.1 Populations

Intention-to-treat (ITT)

All randomised study subjects. This will be seen as the primary population for the analysis.

Per Protocol (PP)

All randomised study subjects completing the whole study period (complete cases). For a specific analysis, study subjects with missing data on any of the variables in the model will be excluded from the analysis. Analyses of this population is seen as a sensitivity analysis to investigate whether conclusions are sensitive to assumptions regarding the pattern of missing data.

6.2 Groups:

Patients with with vitamin-D deficiency are divided into two groups i.e placebo group and vitamin-D group.

Placebo group: out of total 95 participants 47 participants were on placebo arm

Vitamin-D group:

Similar out of total 95 participants 48 participants were on vitamin-D arm

Vitamin-D deficiency:

All randomized study subjects will be divided into two subgroups according to having vitamin-D deficiency at baseline visit.

Division of groups:

All randomised study subjects will be divided into two subgroups according to treatment.

7. Analyses

All outcomes will be presented using descriptive statistics. As the sample size is low so we will check the normality of each variable on screening (Visit 1) and according to the normality check we will determine the mean difference change in Placebo and active treatment arm.

In descriptive analysis we will mention the mean value of each variable with lower and upper bound with 95% confidence interval, 5% trimmed mean, median, Std. Deviation as per the each group ; normally distributed data by the Mean, Variance, Standard deviation (SD), lower and upper values of the variables to see the outliers if any.

In analytical analysis we will apply T-Test for two independent samples to see the difference between two arms. In case any variable doesn't follow the normality assumptions, we will use non-parametric test.

For the safety objective we will use only frequency/number of events to present it.

SPSS 21 will be used for all statistical analysis.

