7.1 Primary outcome

The primary outcome analysis will be performed to check the difference change in Placebo group and Active Treatment group (Vitamin-D Group) through comparing mean difference from Visit 1 to Visit 4. This test will identify the mean increase or decrease in the Vitamin-D levels in the study Participants.

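### The trial is sized on the proportion reaching a vitamin D level at 6 months, but the primary test compares mean change at week 12

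*SAP*

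**What the plan says.** - **Objective and outcome.** SAP 5.1 words the primary outcome as "To determine whether proposed oral high dose vitamin D3 is sufficient for achieving the physiological concentration in HIV positive patients on ART". SAP 3 gives it a time point: "The primary outcome of the study will be the sufficient elevating level of serum 25-hydroxyvitamin D at 24weeks".
- **Sample size.** SAP 3.1 starts from "Assuming that 60% of patients in the control arm would attain > 30% of their baseline vitamin-D status at 6 months" and aims to "detect a 25% absolute increase (to 85%) in the proportion of patients attaining > 30% vitamin-D level at 6 months". It asks for 94 completers (47 per arm) for 80% power at the 5% level, inflated to 114. The protocol abstract gives 104.
- **Primary analysis.** SAP 7.1 works "through comparing mean difference from Visit 1 to Visit 4". SAP 7 names the test: "In analytical analysis we will apply T-Test for two independent samples to see the difference between two arms", with a non-parametric test if normality fails.
- **Analysis set.** SAP 6.1 defines intention-to-treat as "All randomised study subjects. This will be seen as the primary population for the analysis". SAP 6.2 then describes 95 participants, split 47 and 48.
- **Measurement.** Both schedules put Visit 4 at week 12 and Visit 5 at week 24, and mark vitamin D at screening and Visit 4 only. Protocol 5 says "25-hydroxyvitamin D concentration will be measured 0 and 60 days".
- **Protocol analyses.** Protocol 7 assigns the 24-week primary outcome to linear regression adjusted for baseline, reserves a log-binomial model for categorical clinical outcomes, and also names a Wilcoxon test. Protocol 4.4 mentions logistic regression without a threshold.

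**The concern.** The quantity that was powered and the quantity that will be tested differ in type (proportion against mean change) and in time (6 months against week 12). Two things are at stake.

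First, the plan's only power statement would not apply to its primary test. Second, the objective is about sufficiency, meaning whether patients arrive in the physiological range. A difference in means can be significant while most treated patients stay below the range, so the planned primary result would not support the conclusion the trial is set up to draw.

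The responder criterion in SAP 3.1 is also not one that an analyst could code. It is expressed once relative to baseline and once as a percentage level within the same sentence, and never as a concentration.

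**Working it through.** **1. Reproduce the plan's figure.** Inputs from SAP 3.1: 60%, 85%, 80% power, 5% level (two-sided assumed). With unpooled variance:

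n = [0.60×0.40 + 0.85×0.15] × (1.960 + 0.842)² / 0.25² = 0.3675 × 7.849 / 0.0625 = 46.15, so 47 per arm and 94 in total.

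This matches, so the 80% belongs to a comparison of two proportions. (The pooled-variance formula gives 48.88, so 49 per arm.) Exact power at 47 per arm is 79% for the uncorrected chi-square test and 72% for Fisher's test.

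**2. Power of the planned t-test.** Neither document gives an SD or a target mean difference, so power can only be shown against the standardised difference d (in SDs of the change). Noncentral t, 47 per arm, two-sided 5%:

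| d | Power |
|---|---|
| 0.3 | 30% |
| 0.4 | 48% |
| 0.5 | 67% |
| 0.584 | 80% |
| 0.6 | 82% |

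**3. Can 60% versus 85% be carried over to the t-test?** Only with assumptions. If final levels are normal with equal SDs and a common cut-off, the shift is z(0.85) − z(0.60) = 1.036 − 0.253 = 0.783 SD of the level. With baseline correlation ρ, d for the change is 0.783/√(2(1−ρ)):

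| ρ | d | Power |
|---|---|---|
| 0 | 0.554 | 76% |
| 0.1 | 0.584 | 80% |
| 0.2 | 0.619 | 84% |
| 0.4 | 0.715 | 93% |
| 0.6 | 0.876 | 99% |

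If the 0.783 SD shift is placed on the change itself, power is 96%. The mismatch therefore does not show that the trial is underpowered.

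**4. What a mean difference says about attainment.** Assume normal levels, equal SDs and ρ = 0.5, so that the SD of the change equals the SD of the level. A true difference of 0.584 SD then moves attainment from control rate p to Φ(z(p) + 0.584): from 10% to 24%, from 20% to 40%, or from 60% to 80%. This illustrates what is possible; it is not a forecast.

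**5. Power of the attainment test in the all-randomised set.** Implied attrition is 1 − 94/114 = 17.5%. If missing values counted as failures, the rates become 0.60×0.8246 = 49.5% and 0.85×0.8246 = 70.1%. Exact power, uncorrected chi-square:

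| Randomised | None missing | 17.5% missing, counted as failures |
|---|---|---|
| 114 (57 per arm) | 87% | 61% |
| 104 (52 per arm) | 84% | 60% |

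**6. The criterion.** Read literally, exceeding 30% of the baseline value counts as a success a patient who ends at 31% of baseline, a fall of 69%.

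**7. The time point.** SAP 3 and 3.1 say 24 weeks or 6 months. SAP 7.1 says Visit 4, which both schedules place at week 12, while the visit list in protocol 6.1 places Visit 4 at Day 7. Protocol 5 says 60 days. Neither schedule marks vitamin D at week 24.

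**The case against.** The strongest reply is that no loss of power has been shown. Under the bridging model in step 3, the planned t-test has about 80% power or more at any baseline correlation from 0.1 upward. That stands: the fault is that the power is unstated for the planned test, not that it is known to be low.

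The 61% depends on a missing-as-failure rule that neither document adopts, and on an attrition rate inferred from 94 and 114. That also stands. Applying 17.5% to the protocol's 104 borrows the rate from the SAP. If 94 completers were wanted from 104, attrition would be 1 − 94/104 = 9.6%, the rates 54.2% and 76.8%, and exact power 69%. These are conditional figures.

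The 69% fall is unlikely to be what the authors meant, since nearly all stable controls would then succeed, against an assumed 60%. Agreed, but that leaves the intended criterion unknown.

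There are traces of an attainment analysis. SAP 7 reports group means with confidence intervals, the Performa records vitamin D deficiency and achievement of outcome as yes or no, and protocol 4.4 names logistic regression. Protocol 4.4 and 7 also imply an end-of-study measurement. None of these sets a threshold, plans a between-arm comparison of attainment in the SAP, or adds a week-24 assay to the schedules.

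Finally, a mean comparison is a legitimate endpoint. It is, provided the sample size and the conclusion match it.

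**Conclusion.** The concern holds and should be fixed before the data are analysed. From the text alone: the powered comparison (60% against 85% at 6 months) is not the planned one (mean change to Visit 4), the SAP contains no between-arm analysis of attainment, and the schedules provide no vitamin D value at 24 weeks. The arithmetic in SAP 3.1 is correct for the test it describes.

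Power for the planned t-test is not derivable from the documents. It is 80% at 0.58 SD of the change with 47 per arm, and may be higher or lower. The figures in steps 3 and 4 rest on assumed normality, equal SDs and the stated correlations; those in step 5 rest on the inferred attrition rate and the stated treatment of missing values. The main consequence is interpretive: as written, the primary test cannot by itself establish that the regimen is sufficient.

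**What to change.** 1. **Define attainment.** In SAP 5.1 and 7.1, define it as 25(OH)D at or above one absolute ng/ml threshold chosen by the sponsor, fix it before allocation is revealed, and use the same threshold in SAP 3.1. Compare proportions between arms (risk difference or risk ratio with 95% CI) in all randomised patients, with a stated rule for missing values. Keep baseline-adjusted mean 25(OH)D as a supporting analysis.
2. **Settle the time point.** Either restate the endpoint and SAP 3.1 for Visit 4 (week 12), or correct both schedules if a week-24 sample is intended. Align protocol 5 and the Day 7 entry in the visit list, and reconcile the two schedules on sampling at Visit 4: the protocol's adds one day, the SAP's does not.
3. **State power** for the test, analysis set and missing-data rule actually used.
4. **Equally valid alternative:** keep mean change as primary, replace SAP 3.1 with a calculation from a stated mean difference and SD, and limit the conclusion to a difference in mean level.
5. **Reconcile the numbers:** 104 (protocol) with 114 (SAP), and explain the 95 in SAP 6.2 against the all-randomised population in 6.1.

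**Cost.** With a week-12 endpoint: rewording plus one extra analysis of data already scheduled. A week-24 endpoint adds one vitamin D sample and assay per patient. Stated power may become less favourable, down to about 61% with 114 randomised if missing values count as failures at the implied 17.5%.
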